Concomitant Medications As it is known that multi-drug maintenance treatment is the rule rather than the exception in BD, and in order to increase generalizability of study findings, patients will be permitted to continue other psychotropic maintenance treatments. Maintenance treatments are defined as traditional mood stabilizing drugs (such as lithium, valproate or lamotrigine), or antidepressants that have been continued for at least one month at a stable dosage. Dosing on other concomitant treatments is required to remain unchanged for the duration of the study. Medications for side effects (for example, benztropine) may be given at the discretion of the treating psychiatrist. Hypnotic drugs for insomnia/sleep that have been prescribed for at least 30 days may continue to be administered daily (for example zolpidem) at the same dosage.

CAE: The CAE intervention will be modeled and delivered using procedures used in the CAE + LAI pilots. CAE will be delivered by a trained social worker to optimize generalizability. CAE session will be delivered on the same day (either immediately before or immediately after Maintena injection). Supervision will be conducted with a PhD psychologist who helped develop CAE and training will be reinforced as needed.

Measures and Schedule of Events: Table 2 shows the assessment measures, timeline the measures are given, and other specific procedures in the study. Demographic and clinical variables measured at baseline will include age, gender, race/ethnicity, living situation, cumulative medical burden and socioeconomic status at baseline. As in 2 previous successful studies using the medication + adherence support approach in high-risk SMI (Sajatovic 2012a, Sajatovic 2012b) the primary outcome measure will be adherence as assessed via the Tablet Routines Questionnaire (TRQ)

Adherence: A number of investigators have defined "good" adherence in serious mental illness as missing no more than 20% of medication (Gilmer 2004, Valenstein 2004). In previous studies, we demonstrated that this cut-off is sufficient to detect adherence change over time with CAE (Levin 2014, Velligan 2010). Adherence to Maintena will be assessed using the same injection frequency benchmarks used in the previous CAE-L studies (injection is counted as "adherent" if administered within 7 days of when it is scheduled to be administered).

Barriers assessed include BD knowledge, communication with clinicians, medication routines, and substance use.

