Safety evaluations will include baseline and Week 24/End-of-study basic laboratory evaluations (comprehensive metabolic panel, lipid profile, CBC with differential) and pregnancy testing for women. EKG will be conducted at baseline, week 4 and Week 24/End-of-study. Patient vital signs and weight will be collected at each study visit (baseline/V1, V2, V3, V4, V5, V6, V7, V8). Standardized measures of involuntary movements/ extrapyramidal symptoms will be assessed with the Simpson Angus Scale (SAS), the Barnes Akathisia Scale (BAS), the Abnormal Involuntary Movement Scale (AIMS) and the Extrapyramidal Symptoms Scale-Abbreviated version (ESRS-A). Finally, reported side effects will also be evaluated at each study visit using a form derived from the previous CAE-L studies.

Table 2: Measures and Study Schedule of Events

Visit	Screen	BL/ V1	V2	V3	V4	V5	V6	V7
Timing [†]	-14 d to -1d	0 W	4W	8W	12W	16W	20W	24W
Informed consent	X							
Inclusion/Exclusion	X							
Adherence Behavior: TRQ LAI Injection Frequency*	X	X	X	X	X	X	X	X
Non-psychotropic drug TRQ	X				X			X
MINI	X							
CAE module allocation and assessment of Adherence barriers	X							X
Physician Exam and interview	X							X
Demographics, medical burden	X							
Laboratory testing	X				X			X
EKG	X		X					X
Adherence Attitudes: DAI, AMSQ		X			X			X
Symptoms: BPRS, YMRS, MADRS, CGI	X†	X			X			X
Functioning: SOFAS, GAF		X						X
Health resource use		X						X
Alcohol/Substance Use: AUDIT, DAST-10		X			X			X
Trails A & B, Animal Fluency	X							X
Weight and vitals		X	X	X	X	X	X	X
Reported Side Effects		X	X	X	X	X	X	X
Extrapyramidal symptoms: AIMS**, SAS, BAS, ESRS-A	X	X	X	X	X	X	X	X
Patient Satisfaction					X			X
Research Clinician assessment		X	X	X	X	X	X	X
CAE sessions		X	X	X	X	X	X	X
Oral aripiprazole Dispensing***	X	X						
LAI Injection		X	X	X	X	X	X	X

[†]Timing of visits is approximate.

* LAI Injection frequency will be calculated at weeks 12 & 24.

** AIMS will only be administered at BL and W24/Term

*** Dispensing of oral medication is patient specific and may include a 14-day oral tolerability test prior to first LAI injection, or dispensing of anti-side effect medications.

† BRPS will be the only symptom evaluated at screen

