Sample Size and Power: We propose to enroll 30 individuals with BD who receive Maintena +. Based on our prior studies (Sajatovic 2012a, Sajatovic 2012b), we conservatively assume 20% of participants will discontinue study participation during the 24 week study period and that the effect size of CAE-L will be similar to that of CAE-L in prior studies (effect size $d=.60$). Type I error level of 0.05 will be adopted for all tests.

The primary outcomes measure will be change in adherence behavior and the mean LAI injection frequency at 6-months. Adherence rates will be calculated for TRQ in the following manner: the number of days with a missed dose will be divided by the number of days in the time period and then multiplied by 100. Adherence rates will be calculated for both the week and the month prior to assessment visit and for the study period. Given a sample size of 30 subjects with 20% attrition and two-sided Type I error of 0.05, for paired t-tests we will have power of 0.80 for effect sizes of at least 0.597. For correlations, power of 0.80 is achieved for a two-sided test of correlation being zero when the magnitude of correlation is at least 0.51. Hence, there is sufficient power to detect moderate level mean differences and correlation values. For the assessment of mean injection frequency, suppose 6 prescribed injections in 6 months, with a standard deviation of 1.2 (20% of prescribed injections). Then, if a sample mean of 5.28 or higher is observed (88%), a 95% two-sided confidence interval will not contain 4.8, the 80% threshold, This would provide evidence that the percentage of injection frequency is higher than 80%. Note that adherence levels of 80% or higher are widely considered to be "acceptable" adherence in the research literature. The mean LAI injection frequency in our previous pilot work involving LAI + CAE in homeless patients with schizophrenia exceeded 90% of prescribed injections at 6-month follow-up. We thus expect to statistically establish that the mean LAI injection frequency in this bipolar sample who are not homeless is above the 80% threshold.

Data analyses will be performed using the Statistical Analysis System (SAS) (SAS Institute, Cary, NC, 2002).. For Aim 1, change in TRQ from baseline to 24 weeks will be assessed with a paired t-test or Wilcoxon signed rank test. For mean LAI injection frequency, we will construct 95% confidence intervals. Exploratory longitudinal

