models of adherence will be considered as well. We may represent adherence as a binary outcome, indicating whether or not an adherence threshold has been met (e.g., 80% adherent), particularly if adherence levels are highly skewed. Exploratory logistic regression through generalized estimating equations (GEE) or generalized linear mixed models for binary outcomes will thus be considered for assessing effects of time. Time may be modeled with a slope parameter or treated as a categorical variable. Age, race, duration of illness, and/or gender will be considered as possible covariates. In addition, we will compare corresponding TRQ and SimpleMed pillbox adherence levels. Correlation between the adherence measures will be estimated and Bland-Altman plots will be generated (Altman 1983).

Aim 2 will evaluate change from baseline to 24 weeks in TRQ, psychiatric symptoms (BPRS, MADRS, YMRS, CGI) in a similar manner as in Aim 1. For Aim 3, change in the outcome variables and other secondary measures in the proposed study vs. historical controls (the previously conducted CAE + LAI pilots) will be compared through effect sizes. In Aim 4, adherence barriers will be evaluated as well. Mean change in symptom rating scales, functional level and medication attitudes will be estimated from baseline to the various follow up periods. We will explore whether reductions in adherence barriers (e.g., BD knowledge, medication routines, communication, and substance) will be associated with changes in adherence behavior. Correlations between respective changes in barriers and adherence levels will be computed. In a similar manner, we will also examine whether improvements in adherence behaviors correlate with improvements in symptoms, functioning, and medication attitudes.

Study reporting/deliverables: Reporting on study outcomes will be focused on rapidly available and impactful findings. As the study does not require blinding, it is expected that interim results can be used for new research abstract proposals that can be submitted even while the study is ongoing. It is expected that study results will be presented at a minimum of 2-3 suitable scientific venues including (but not limited to):

- American College of Neuropsychopharmacology (ACNP)
- American Psychiatric Association (APA)
- International Society for Bipolar Disorders (ISBD)

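### The Aim 1 and Aim 2 tests use only patients with a week-24 value, so in this single-arm trial of poorly adherent patients the reported improvement may be too large for all enrolled

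*Combined protocol and SAP*

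**What the plan says.** Under Data Management & Analyses, the primary TRQ test is: "For Aim 1, change in TRQ from baseline to 24 weeks will be assessed with a paired t-test or Wilcoxon signed rank test". The symptom scales follow the same method as the first aim: "Aim 2 will evaluate change from baseline to 24 weeks in TRQ, psychiatric symptoms (BPRS, MADRS, YMRS, CGI) in a similar manner as in Aim".

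Sample Size and Power sets enrolment ("We propose to enroll 30 individuals with BD who receive Maintena") and attrition: "we conservatively assume 20% of participants will discontinue study participation during the 24 week study period". The power figure follows from these: "Given a sample size of 30 subjects with 20% attrition and two-sided Type I error of 0.05, for paired t-tests", power is 0.80 at an effect size of 0.597 or more. The effect size assumed from prior studies is d = 0.60.

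Table 2 schedules the measures as follows:
- TRQ: every visit.
- Symptom and attitude scales: baseline, week 12 and week 24 (BPRS also at screening).
- SOFAS and GAF: baseline and week 24 only.

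Termination wording is attached to few items. The AIMS footnote says: "AIMS will only be administered at BL and W24/Term". The Safety Evaluations section uses a week-24-or-end-of-study label for laboratory tests and EKG.

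Two further provisions bear on the point. Longitudinal models of adherence are described as exploratory and as something to be considered. Mean changes in symptoms, functioning and attitudes are to be estimated from baseline to the various follow-up periods, with no rule for missing values.

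**The concern.** A paired test drops any patient without a week-24 value. The plan expects six of 30 to discontinue, and it does not say who is analysed, how a missing value is treated, or whether a patient who stops injections is still assessed. Followed as written, Hypotheses 1 and 3 and the effect sizes carried into Aim 3 describe the patients who stayed.

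That matters more here than in many small studies. Patients enter because they miss medication, the primary outcome is adherence, and there is no control arm whose own dropout could offset the selection. If those who leave tend to be those who did not improve, the completer mean is too favourable for the group enrolled. Meanwhile the TRQ values that stoppers gave before leaving are not used in the primary test.

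**Working it through.** **Inputs from the documents**
- Enrolled: 30. Attrition: 20%. Two-sided alpha: 0.05. Detectable effect: 0.597 at power 0.80. Assumed d: 0.60 (all from Sample Size and Power).
- Injection-frequency threshold: 5.28, with SD 1.2 and reference value 4.8 (same section).
- Early termination in the second LAI + CAE pilot: 4 of 30, or 13.3% (Background).

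**Step 1. Reproduce the plan's figure.** Pairs remaining: 30 × 0.8 = 24. Paired t-test power from the noncentral t distribution with n − 1 degrees of freedom and noncentrality d√n:
- n = 24, d = 0.597: power 0.7998.
- n = 30, d = 0.597: power 0.885. The detectable effect at 0.80 power would be 0.529.

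So 0.597 comes from 24 pairs. The injection threshold agrees: 4.8 + 1.96 × 1.2/√24 = 5.280, whereas 30 patients would give 5.229.

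**Step 2. Effect across all enrolled.** Assume that all 30 receive a first injection, that completers improve by 0.60 SD, and that stoppers have zero change. With dropout proportion p:

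all-enrolled mean = (1 − p) × 0.60; overstatement = 1/(1 − p) − 1

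| Dropout | All-enrolled mean | Completer mean too large by |
|---|---|---|
| 13.3% (4 of 30) | 0.52 SD | 0.60/0.52 − 1 = 15% |
| 20% (6 of 30) | 0.48 SD | 0.60/0.48 − 1 = 25% |

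**Step 3. Power of a no-change analysis at 20% dropout.** With six zero changes:
- SD = √(0.8 + 0.8 × 0.2 × 0.60²) = √0.8576 = 0.926.
- Standardized effect = 0.48/0.926 = 0.518.
- Power at n = 30 = 0.78, against 0.80 for 24 pairs at d = 0.60.

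**Step 4. Significance at an observed completer d of 0.60.**
- Completers: t = 0.60 × √24 = 2.94 on 23 df, p about 0.007.
- All 30 with six zeros: sample SD = √[(23 + 24 × 0.12² + 6 × 0.48²)/29] = 0.923; t = 0.48/(0.923/√30) = 2.85 on 29 df, p about 0.008.

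**Step 5. How far stoppers would have to move to cancel the effect.** Setting 0.8 × 0.60 + 0.2 × m = 0 gives m = −2.4. The six stoppers would have to worsen by 2.4 SD on average.

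**The case against.** The strongest reply is that the plan is less bare than it looks. The label in "AIMS will only be administered at BL and W24/Term" may simply be the name of the V7 visit. The AIMS row is marked at every visit and so needed a footnote limiting it. On that reading, the whole V7 column, including TRQ, symptoms and functioning, is done when a patient leaves early. A reader might infer from the labels that only safety measures are taken at termination, and hence that a patient leaving at week 8 yields no symptom data after baseline. The text does not establish that. What stands is that the plan never says so for the efficacy measures, and no rule says how a termination value enters a baseline-to-week-24 test.

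The plan also provides descriptive symptom estimates at other follow-ups and exploratory longitudinal models, and its co-primary injection frequency responds directly to stopping. These provisions are real. But the models are optional and cover adherence only, the symptom estimates are descriptive, and none of them changes who enters the Aim 1 and Aim 2 tests.

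A reader might also take "Dosing on other concomitant treatments is required to remain unchanged for the duration of the study" to mean that patients who worsen and need a dose change are withdrawn. No passage says that a change leads to withdrawal, so the point does not rest on it.

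Finally, a mixed model is no cure for informative dropout, because it assumes data are missing at random. TRQ is bounded, and the plan itself anticipates skewed adherence. That is a fair reason not to require such a model in place of the planned primary test.

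**Conclusion.** The point holds in a limited form. As written, the Aim 1 and Aim 2 tests give a completer result, and the plan's own power figure confirms that it was built on 24 patients.

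Whether that result overstates the benefit depends on outcomes in stoppers, which the documents do not give. If stoppers do not change, the overstatement is 15% to 25% over the range from the pilot's dropout to the plan's. If stoppers gain something, it is smaller; if they worsen, it is larger. A reader might infer that the improvement is certainly inflated, or that it could be wholly an artefact of selection. The documents do not support either. At 20% dropout with unchanged stoppers, the result at d = 0.60 stays significant, and cancelling it would take an implausible deterioration. The issue is the size of the reported effect and whom it describes. It is worth correcting before analysis.

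**What to change.** 1. For Aims 1 and 2, define the analysis set as all patients who received a first injection. Prespecify a sensitivity analysis that sets patients without a week-24 value to no change from baseline, and report it beside the week-24-pair result. Zeros for stoppers also shrink the SD, so this shows one plausible case and is not a worst-case bound.
2. Prespecify, as a supportive analysis, a repeated-measures model of TRQ using every scheduled visit, with its missing-at-random assumption stated. The paired t or Wilcoxon test can remain primary.
3. State in Table 2 that the V7 TRQ, symptom, functioning and attitude assessments are also attempted at early termination and recorded at their actual week. State too that scheduled TRQ and outcome collection continues where possible after injections stop. This concerns data collection only and changes nothing in clinical management.

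The cost is protocol wording, a modest amount of analysis, and an existing assessment battery for about six patients. The reported effect may be smaller, and the sensitivity test has about two points less power than the paired test.

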An important limitation of the CAE-L pilots is that they excluded individuals with BD. The pilot studies combined LAI + CAE data suggested that patients with schizoaffective disorder (N=44) did just as well as those with schizophrenia (N=16) with respect to adherence, symptom and functional outcomes (Levin et al., 2017). Combining Maintena with a practical method of adherence support has potential to enhance uptake and optimize enduring adherence to medication in patients with BD.

Project Design:

Overview: 6-month, prospective, trial testing the effects of Maintena augmented with CAE in 30 poorly adherence patients with BD. After a 2-month study start-up period, patients will be enrolled over a 16 month enrollment period (months 2-18). The targeted enrollment of approximately 2 participants/month is reasonable given previous recruitment with the CAE + LAI pilots. Primary outcomes will be change from baseline in adherence as identified by the Tablet Routines Questionnaire (TRQ) and injection frequency at the 6-month time-point. We will also evaluate changes in secondary outcomes, including BD symptoms (BPRS), depressive and global psychopathology symptoms, functional status, and adherence attitudes. Additional exploratory assessments will include health resource use, adherence barriers, substance use and neurocognition. Outcome measures will be assessed at Screening, Baseline, and Weeks 4- 24 as noted in Table 2/Study Schedule of Events. Because the study design will be nearly identical to the 2 previously conducted CAE + LAI pilots, it will be possible to compare primary and secondary outcomes of this study of individuals with BD to individuals with schizophrenia/schizoaffective disorder. The study will be operationalized in 4 specific Aims:

Aim 1: Test whether combined Maintena + CAE (Maintena +) is associated with improved treatment adherence

[figure not shown]
Hypothesis 1: At 6-month follow-up, poorly adherent BD patients receiving Maintena + will have significant improvement in medication adherence as measured by the TRQ.

Hypothesis 2: At 6-month follow-up we also expect that mean LAI adherence as measured by injection frequency will meet or exceed 80%. The 80% threshold is widely viewed in the treatment adherence literature as an “acceptable” degree of adherence.

Aim 2: Test whether Maintena + is associated with reduction in BD symptoms, improved functioning and better treatment attitudes

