2. Known to have medication treatment adherence problems as identified by the Treatment Routines Questionnaire (TRQ, 20% or more missed medications in past week or past month)
3. Screening BPRS score of ≥ 36
4. Ability to be rated on psychiatric rating scales.
5. Willingness to take LAI
6. Currently in treatment or scheduled to receive treatment at a Community Mental Health Clinic (CMHC) or other clinical setting able to provide mental health care during and after study participation
7. Able to provide written, informed consent to study participation.

Exclusion Criteria:

1. Individuals on LAI immediately prior to study enrollment.
2. Individuals with known intolerance or resistance to either oral aripiprazole or LAI formulation of aripiprazole
3. Prior or current treatment with clozapine
4. Medical condition or illness, which in the opinion of the research psychiatrist, would interfere with the patient's ability to participate in the trial
5. Physical dependence on substances (alcohol or illicit drugs) likely to lead to withdrawal reaction during the course of the study in the clinical opinion of the treated research psychiatrist
6. Immediate risk of harm to self or others
7. Female who is currently pregnant or breastfeeding

Study Medication: Medication dosing will follow recommendations in the Maintena package insert. For patients who have never received aripiprazole, there will be a brief oral tolerance testing (OTT) of up to 14 days. Individuals who tolerate OTT will then receive 400 mg of Maintena administered IM in the gluteal or deltoid location, and oral Abilify will continue for an additional 14 days, after which oral medication will be discontinued. After the initial IM injection, individuals will continue to receive injections of Maintena every month for a total of 6 months. The standard dosage of 400 mg IM will be administered in this maintenance treatment phase although clinicians may administer a lower dosage of 300 mg IM depending on clinical response.

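### Injection frequency is to be shown above 80%, but the plan does not say who enters the mean or whether injections due after a patient stops stay in the denominator; the claim can depend on that choice.

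*Combined protocol and SAP*

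**What the plan says.** The Project Design overview and Sample Size and Power both list injection frequency at 6 months as a primary outcome beside the TRQ. Measures and Schedule of Events names only the TRQ as the primary measure. Hypothesis 2 under Aim 1 expects that "mean LAI adherence as measured by injection frequency will meet or exceed 80" percent.

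Sample Size and Power supplies the numbers:
- Attrition: "we conservatively assume 20% of participants will discontinue study participation during the 24 week study period".
- Denominator and spread: "suppose 6 prescribed injections in 6 months, with a standard deviation of 1.2".
- Cut-off: "if a sample mean of 5.28 or higher is observed (88%), a 95% two-sided confidence interval will not contain 4.8", where 4.8 is 80% of 6.
- Analysis: "For mean LAI injection frequency, we will construct 95% confidence intervals".

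The Adherence paragraph says Maintena adherence will use the benchmarks of the previous CAE-L studies. It restates one rule, that an injection counts as adherent "if administered within 7 days of when it is scheduled to be administered". A Table 2 footnote adds "LAI Injection frequency will be calculated at weeks 12 & 24".

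On the number of injections, Study Medication says "individuals will continue to receive injections of Maintena every month for a total of 6 months" after the initial one. That can be read as 6 in all or as 6 after the first. The LAI Injection row of Table 2 is marked at seven visits, weeks 0 to 24.

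**The concern.** Two choices are open: which patients enter the mean, and whether an injection that falls due after a patient has stopped still counts as scheduled. The 7-day window deals with lateness and settles neither. At least three analyses fit the wording: completers only, all patients over injections due while enrolled, and all patients over a fixed denominator.

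These do not estimate the same thing. In a trial of adherence to an injection, stopping the injections is close to the failure being measured. The first two analyses leave most of that failure out and would tend to report a higher figure. With a single arm compared against a fixed 80%, no control group carries the same tendency and cancels it. The study is also unblinded, and Study reporting/deliverables foresees abstracts from interim results, so an unwritten rule could be settled after results have been seen.

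**Working it through.** **1. The plan's own cut-off.** The observed mean must reach 4.8 + q × 1.2/√n, where q is the 97.5% quantile.

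| n | normal quantile | t quantile |
|---|---|---|
| 24 (30 less 20%) | 5.280 | 5.307 |
| 30 | 5.229 | 5.248 |

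The stated 5.28 is reproduced at n = 24 with the normal quantile: 4.8 + 1.96 × 1.2/√24 = 5.280. It is not reproduced at n = 30. A t interval at n = 26 gives 5.285, so the match is not unique.

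**2. Illustration.** From the documents: 30 patients, 20% discontinuing (6), 6 injections, SD 1.2, threshold 80%, and the pilot mean of 90.5% at week 25 (Table 1). Assumed, because the documents do not say:
- 90.5% (5.43 of 6) and SD 1.2 describe the 24 completers;
- all six patients who stop have had a first injection;
- each of them receives k of 6, with no spread among them.

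Intervals are t-based.

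*Completers only:* 5.43 ± 2.069 × 1.2/√24 = 4.923 to 5.937, that is 90.5% (82.1 to 98.9). 80% is excluded.

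*All 30, injections due while enrolled*, if those who stop received every one of theirs: (24 × 90.5 + 6 × 100)/30 = 92.4%; SD = √[(23 × 20² + 4.8 × 9.5²)/29] = 18.2; interval 85.6 to 99.2. 80% is excluded.

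*All 30, fixed denominator, later injections not adherent:* mean = (24 × 5.43 + 6k)/30; SD = √{[23 × 1.2² + (24 × 6/30)(5.43 − k)²]/29}. For k = 3 the mean is 4.944, the SD is 1.456, and the interval is 4.944 ± 2.045 × 1.456/√30 = 4.400 to 5.488.

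| k of 6 | mean | 95% CI | excludes 80%? |
|---|---|---|---|
| 1 | 75.7% | 62.7 to 88.8 | no |
| 2 | 79.1% | 68.1 to 90.0 | no |
| 3 | 82.4% | 73.3 to 91.5 | no |
| 4 | 85.7% | 78.2 to 93.3 | no |
| 5 | 89.1% | 82.3 to 95.8 | yes |

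The lower limit reaches 80% at k of about 4.4. The mean itself falls below 80% when k is under (144 − 130.32)/6 = 2.28.

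**3. Sensitivity.**
- With 4 patients stopping (13.3%, as in the second CAE-L pilot), the break-even k is about 4.1. With 3 it is about 3.8.
- With 6 stopping and a completer SD of 0.8, it is about 4.0.
- With 7 scheduled injections (completers at 90.5%, SD 1.4, threshold 5.6), it is about 5.2 of 7, the same 74%.
- With completers at 95% and k = 4, the result is 89.3% (81.4 to 97.3), which excludes 80%.
- If 90.5% and SD 1.2 already describe all 30 patients, the interval is 5.43 ± 2.045 × 1.2/√30, or 83.0 to 98.0%, which excludes 80%.

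**The case against.** Several points on the other side have force.

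- **The rule may exist by reference.** The Adherence paragraph points to the previous studies' benchmarks, and those reports may say how stopped patients were counted. The fair claim is that these documents do not restate such a rule. It still needs writing here, because the plan should be usable without those reports.
- **The wording leans towards a fixed denominator.** A count out of 6 prescribed injections, and an SD given as a percentage of prescribed injections, suggest it. This stands, but it does not say whether patients who stop are in the mean.
- **A reader might infer from the n = 24 match that a completers-only analysis is intended.** The documents do not support that. The same paragraph states its paired t-test power for 30 subjects with 20% attrition, and allowing for attrition in a precision calculation is routine.
- **The base case may penalise stopping twice.** Table 1 does not call 90.5 a completer figure. It has N = 50 under a heading of 60 patients, so ten may have been left out. Its SD is 30.1. If that is in percentage points on a 0 to 100 scale, it is about as large as it can be (√(90.5 × 9.5 × 50/49) = 29.6). Values would then be close to all-or-none, and some patients may already be scored near zero. The pilot figure may or may not include patients who stopped. Nor does the plan restrict SD 1.2 to completers.
- **Six injected patients who stop is an upper bound under the 20% assumption.** Oral tolerability testing can precede the first injection, and anyone leaving then would not be in an all-injected set.
- **Adherence while enrolled is a legitimate target.** That is true, and it should be reported. As the sole basis for a claim about sustained adherence, it omits the patients who did not sustain it.

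**Conclusion.** The gap is real and should be closed before analysis. The current text allows analyses that would tend to overstate adherence, and it leaves the injection count at 6 or 7.

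A reader might infer that the 80% conclusion turns into a failure. The calculations do not show that. In the k = 3 illustration the mean stays above 80%, so the expectation in Hypothesis 2 is still met as a point estimate. What is lost is the interval excluding 80%, which is what Sample Size and Power relies on to establish the claim statistically. No interval shown falls wholly below 80%.

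The loss is possible, not certain. It rests on the assumed completer mean and SD, on up to six injected patients stopping, and on their averaging fewer than about 4.4 of 6 injections. The documents give no timing of discontinuation. The 5.28 is not an arithmetic error; it needs its n and quantile stated.

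**What to change.** 1. Reconcile the number of scheduled injections across Sample Size and Power, Study Medication and Table 2, and state whether the first one counts. If the analysis set requires a first injection, counting it gives every patient one adherent injection by construction.
2. Define the primary injection analysis as all patients who receive a first injection, over a fixed denominator of all injections scheduled through week 24. Injections not given after discontinuation count as not adherent.
3. Use a t-based interval and restate the cut-off for that n and SD. With 6 injections and SD 1.2 it is 5.25 (87.5%) at n = 30 and 5.31 (88.4%) at n = 24, against the stated 5.28. If the SD over all patients were 1.46, as in the k = 3 case, it would be 5.34 (89.1%) at n = 30.
4. Report as secondary: completers only, injections due while enrolled, and a version that counts injections documented as given elsewhere. List the reasons for stopping.

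The planned TRQ test is unaffected. The cost is a few sentences of analysis text, essentially on data already being collected. The downside is a probably lower headline percentage and a wider interval, so the 80% claim is harder to meet with 30 patients. The rule is also strict for patients who leave for reasons other than non-adherence, which is why item 4 is needed.
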